### 3.5 Data Sources

Sources of data for this study include the participant baseline and follow-up assessments, provider semi-structured interviews, audio recordings of counseling sessions that will be rated for fidelity, and medical record data (to collect HIV appointment attendance and viral loads). We will capture viral load from medical records when possible; if no viral load is scheduled at the requisite time point for the study, then the study will order and pay for a viral load test. Blood samples for study viral loads will be drawn by the same clinic staff and in the same manner as clinic-ordered viral loads

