**Secondary Outcomes:** Secondary outcomes will be used to provide preliminary information about effectiveness, taking into consideration the limited sample size for the pilot project. *HIV-related outcomes* (the primary outcomes for the eventual full-scale trial) will be defined as (a) *viral suppression at 6 months*, and (b) HIV appointment adherence between baseline and 12 months of follow up. Viral load will be captured from clinical records, or ordered by the study if no viral load is collected in the appropriate window. HIV appointment attendance will be evaluated by measuring the proportion of scheduled visits in the 12-month follow-up period that are attended vs. no-shows (the “kept visit proportion”), with no show defined as no appointment kept in the 30 days following a scheduled appointment. HIV appointment data will be abstracted from clinic records at the end of the study period.

*Mental health outcomes* (the secondary outcomes for the eventual full-scale trial) will be defined as DASS-21 total score indicating any CMD symptoms as well as mean subgroup scores for depression, anxiety, and stress at 6 weeks after enrollment (FB: treatment exit) across all study arms. We will consider both the simple severity level at follow-up as well as the absolute reduction in symptoms from baseline.

*Methadone maintenance engagement* (another secondary outcome for the full trial) will be defined as the proportion of days with methadone maintenance therapy adherence measured from study baseline through 12 months of follow up.

**Additional (tertiary) outcomes:** Tertiary *HIV-related outcomes* will be defined as (a) viral suppression at 12 months and (b) consistent ART use over 12 months as confirmed by clinical records. Tertiary *mental health outcomes* will be defined as DASS-21 total score indicating any CMD symptoms as well as subgroup scores for depression, anxiety, and stress at 3 months, 6 months, and 12 months across all study arms. We will consider both the simple severity level at follow-up as well as the absolute reduction in symptoms from baseline.

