### **3.4 Sample Size**

A total of 75 patients will be enrolled over time, recruited over a three-month period in year 2.

We recognize that the purpose of a pilot trial with limited sample size is not to be fully powered to detect statistically significant differences on patient outcomes but rather to provide reasonably precise estimates of parameters such as acceptability and fidelity, as well as preliminary evidence of the likely magnitude of effect of the intervention on the outcomes planned for the later trial. Assuming 80% retention (consistent with our team's previous work in this population), our starting sample size of 50 intervention participants is sufficient to estimate parameters such as the proportion of participants rating the intervention as acceptable with a 95% confidence interval of  $\pm 10$ -15 percentage points, and parameters such as the proportion of FB sessions with acceptable fidelity with a 95% CI of  $\pm 6$ -8 percentage points. Our starting sample size of 25 participants in each arm, with 80% retention, is sufficient to estimate risk ratios of the effect of the intervention on outcomes that have 95% CIs that are two- to three-fold wide (e.g., RR=0.63; 95%CI = 0.38-1.00 for the presence of elevated symptoms), depending on various assumptions about outcome frequency. For comparison of effect sizes, we note that the 24-clinic cluster-randomized trial of the FB found effect sizes much stronger than this (adjusted risk ratios of 0.21 [0.15-0.29] for presence of any symptoms and 0.28 [0.22-0.34] for presence of depressive symptoms). Thus the sample size is adequate to achieve our aims.

IRB# 20-1689

Protocol v3.0 2023-10-01

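### Sections 3.0 and 3.5 give different triggers for the study-ordered viral load, and a scheduled but missed clinic draw is covered by only one of them

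*Combined protocol and SAP*

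**What the plan says.** Two places in the combined protocol and SAP describe how the viral load is obtained.

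- Section 3.0, Secondary Outcomes: "Viral load will be captured from clinical records, or ordered by the study if no viral load is collected in the appropriate window". This paragraph defines "viral suppression at 6 months" as the first HIV-related outcome, secondary in this pilot and intended as a primary outcome of the later full-scale trial. The tertiary outcomes in the same section include "viral suppression at 12 months and (b) consistent ART use over 12 months as confirmed by clinical records".
- Section 3.5, Data Sources: "We will capture viral load from medical records when possible", followed by this condition for a study test: "if no viral load is scheduled at the requisite time point for the study, then the study will order and pay". It adds that clinic staff draw the study samples in the same way as clinic-ordered ones.

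Neither place defines the window around 6 or 12 months or says when staff look at the record. The list of follow-up assessments under Research interviews in section 3.0 includes a urine drug screen at 6 months but no check of the viral load record.

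**The concern.** One rule turns on whether blood was *drawn*, the other on whether a test was *scheduled*. They give different answers for the patient who had a clinic viral load scheduled around month 6 and did not attend. A site working from section 3.5 could conclude that a test had been scheduled, so none needs ordering, and the patient would end with no 6-month value.

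A gap of that kind is unlikely to be random. It would arise from not keeping clinic appointments, and engagement in HIV care is something the intervention is meant to improve. The background in section 1.1 describes low retention and low viral suppression in this population, and section 3.0 makes HIV appointment attendance an outcome with its own no-show definition, so missed appointments are foreseeable. At stake is the usefulness of the pilot's suppression estimates, which section 3.4 intends as preliminary evidence on likely effect size for the next trial.

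**Working it through.** **Step 1: compare the two triggers.**

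| Situation at the time point | Section 3.0 rule | Section 3.5 rule, read literally |
|---|---|---|
| No clinic test scheduled, none drawn | Study test | Study test |
| Clinic test scheduled and drawn in the window | None needed | None needed |
| Clinic test scheduled but not drawn | Study test | Study test not prompted |

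The third row is the one that can lose an outcome. No section ranks one rule above the other.

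**Step 2: see whether the timing rescues it.** The section 3.0 trigger recovers the outcome only if someone looks while the window is open. No section sets that time. The documents do not say the check is late; they leave it open.

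**Step 3: see whether the analysis rescues it.** Section 4.0 compares HIV-related outcomes by intent-to-treat but does not say how a missing viral load is scored. Its missing-data paragraph offers inverse probability weights as a sensitivity analysis if a pattern of missingness is found, and its example is baseline symptom severity. Missed draws would depend on engagement after baseline, which weights built on baseline variables may not capture.

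**Step 4: illustrate the size.** The plan states no figure on this point, so there is none to reproduce. It gives neither the share of draws missed nor suppression among those patients, so both are assumptions:

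- share missing a scheduled draw and left untested: m = 10% to 25%
- suppressed if drawn: 90%; suppressed if missed: 60%

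True suppression = (1 − m) × 0.90 + m × 0.60. Tested patients alone show 0.90, so the overstatement is m × (0.90 − 0.60).

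- m = 10%: true 0.90 × 0.90 + 0.10 × 0.60 = 87.0%; overstated by 3.0 points
- m = 15%: true 0.85 × 0.90 + 0.15 × 0.60 = 85.5%; overstated by 4.5 points
- m = 25%: true 0.75 × 0.90 + 0.25 × 0.60 = 82.5%; overstated by 7.5 points

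With a 40-point gap instead (90% versus 50%, or 80% versus 40%) and m = 10% to 20%, the overstatement is 4 to 8 points. With no gap it is zero at any m.

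**Step 5: between arms.** If m is equal in all arms and the two suppression rates are common to them, the difference between arms is unbiased. If m were 25% under enhanced usual care and 10% in a Friendship Bench arm, the true rates would be 82.5% and 87.0%, a difference of 4.5 points, while tested patients would show 90% in both. That zero is built in by giving drawn patients the same 90% in each arm.

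**Step 6: compare with the pilot's precision.** Section 3.4 gives "Our starting sample size of 25 participants in each arm, with 80% retention", so 25 × 0.80 = 20 per arm.

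- Difference, 87.0% versus 82.5%: 95% half-width = 1.96 × √(0.87 × 0.13/20 + 0.825 × 0.175/20) = 1.96 × 0.113 = about 22 points
- One arm at 82.5%: 1.96 × √(0.825 × 0.175/20) = about 17 points

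Against 20 patients, 4.5 points is 0.9 of a patient.

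**The case against.** The strongest reply is that the missed draw is already covered. Section 3.0 defines the outcome, and a scheduled but missed test has not been collected, so the study orders one. Section 3.5 does not say that a study test is ordered *only* when none is scheduled; it gives one condition and is silent on the missed draw. The two can be read together, with section 3.0 as the backstop. Section 7.0 says these patients come to clinic daily for observed methadone, so a missed draw could be made up quickly. Section 4.0 promises efforts to limit missing data, including locator contacts, and a look at missingness patterns. Suppression is also a secondary outcome of a pilot whose primary outcomes are feasibility, acceptability and fidelity.

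Most of this stands, and it makes the loss conditional. It does not remove the inconsistency: no section says that section 3.0 governs, and staff obtaining viral loads could reasonably work from Data Sources. Daily attendance offers an opportunity to draw blood, but no rule uses it, and methadone adherence is itself an outcome, so full attendance cannot be assumed for the least engaged patients.

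A reader might infer more: that the poorest engagers will lose the outcome, that suppression will be overstated in every arm, and that any effect working through engagement will vanish from the comparison. The documents do not support that. The loss requires a literal use of section 3.5 or a late check. The overstatement requires missed-draw patients to be less often suppressed, which is plausible but not shown. An effect on adherence among patients who are drawn would still be seen.

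**Conclusion.** The two triggers are inconsistent and should be reconciled. The text establishes that a scheduled but missed clinic draw prompts a study test under section 3.0 and not under a literal reading of section 3.5, with no statement of which applies or when the record is checked. It is a reasonable inference, not a finding, that any resulting gaps would fall mainly on less engaged patients.

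The size and direction of any bias cannot be obtained from the documents. The overstatement of 3 to 7.5 points rests wholly on the assumed 10-25% missed draws and 60% versus 90% suppression, and on those patients going untested. Bias between arms further requires unequal missed draws or unequal suppression gaps. These amounts are well within the pilot's imprecision. The reason to act is that the correction is cheap and the outcome is meant to carry the later trial.

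**What to change.** - Amend section 3.5 to the section 3.0 trigger: the study orders a viral load when none has actually been drawn in the outcome window, and a scheduled but missed clinic test counts as not collected.
- Define the 6- and 12-month windows so that each research interview falls before its window closes.
- Have staff check the record at the 6- and 12-month interviews, so that a study sample can still be drawn in the window, at that contact or at a methadone attendance.
- State in section 4.0 how a viral load that is still missing enters the comparison.

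Section 3.3 plans follow-up through December 2022 and this version is dated 1 October 2023, so the draws may already be complete. In that case, state which trigger was applied and report the number of missing viral loads by arm at each time point.

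The cost is a few sentences and some extra study-paid tests of a kind already funded and drawn by clinic staff. Under the assumed 10-25% missed draws, that is at most about 8 to 19 tests per time point (75 × 0.10 = 7.5; 75 × 0.25 = 18.75), and fewer after loss to follow-up. No added visits are needed. The change will not recover patients who are out of contact altogether.

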#### 3.5.1 Record Availability

The site investigator will make all data abstraction documents and records readily available for inspection by the local IRB and the Office for Human Research Protections (OHRP) as requested.

## 4.0 ANALYSIS

**Statistical Analysis.** Feasibility, acceptability, and fidelity will be evaluated using descriptive statistics. We will compare mean fidelity scores between the professional FB and lay FB counselors using an intent-to-treat approach, using a robust variance estimator to account for multiple observations per counselor. Means and proportions for HIV-related and mental health outcomes will be compared between arms using an intent-to-treat analysis approach.

We will evaluate effectiveness measures comparing professional counselors to enhanced usual care and lay counselors to enhanced usual care. Considering the purpose of this small pilot trial, our focus will be on estimating effect size and precision rather than statistical significance and hypothesis testing. To take advantage of the repeated-measures nature of the outcome data, we will also fit generalized estimating equation (GEE) regression models, using a link appropriate for each outcome (i.e. identity link for continuous variables and log link for binary variables), to simultaneously examine differences in outcomes at 6 weeks, 3 months, 6 months and 12 months between the arms. Given the relatively small sample size, it is possible that important predictors of outcome (such as baseline mental health symptom severity or time in HIV care) could end up being unbalanced between arms; if this is the case we will conduct secondary regression analyses adjusting for the unbalanced potential confounder.

In **secondary analyses**, we will examine whether HIV-related, MMT, and mental health outcomes vary by proportion of FB sessions attended and by number of elevated symptom domains at baseline (depression, anxiety, and/or post-traumatic stress).

In **moderation analyses**, we will explore whether severity of illness (duration; symptom severity; family history) modifies any preliminary evidence of efficacy in primary outcomes, while recognizing that a pilot trial is not designed to be powered to statistically test modification hypotheses.

**Missing data.** Every effort will be made to minimize missing data, including collecting detailed locator information for the participant as well as for up to three individuals who could help reach the participant should they drop out of contact. However, some missing

IRB# 20-1689

Protocol v3.0 2023-10-01

data is likely to occur. We will examine the data for patterns of missingness (for example, are the patients with the greatest mental health symptom severity at baseline the most likely to be lost to follow-up?), and if identified, will conduct sensitivity analyses using inverse probability weights to correct for the bias introduced by the missing data.

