Lay counselors may prove effective in delivering FB to PLWH with OUD; indeed, in other work we have demonstrated the effectiveness of peer counselors in improving ART adherence in this population. That said, CMDs may prove more difficult to treat in a population with OUD than among primary care patients, requiring the higher skill level of professional counselors for FB to be effective with this key population. A number of health care professionals in Vietnam have training in counseling, and the MOH could invest in expanding this cadre if evidence suggests that the higher level of training is critical. However, if lay counselors are equally effective then their deployment would be less expensive.

Our **objective** is to complete a pilot randomized trial of 75 patients from 4 MMT clinics where we have worked successfully in the past. We will compare FB delivered by professional counselors and FB delivered by lay counselors vs. enhanced usual care to improve CMDs and HIV care outcomes among PLWH and OUD in Vietnam. This work will

generate critical data to inform a fully powered R01 trial. We **hypothesize** that adapted FB will be acceptable to patients and providers, prove feasible to integrate into MMT clinics, be delivered with fidelity, and demonstrate preliminary indications of impact with both counselor groups.

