**Primary Outcomes:** *Feasibility* will be defined as the ability to successfully enroll and retain PLWH and OUD with CMDs in the pilot intervention. Feasibility will be evaluated by measuring the recruitment rate (number of patients approached to accrue the final sample). Additional indicators of feasibility will include study retention, defined as the ability to retain PLWH and OUD with CMDs in the pilot trial. Study retention will be evaluated by measuring the number of participants retained in the study (number of patients enrolled at baseline who are still enrolled in the trial), through study completion. An additional measure of intervention feasibility will be defined as the number of FB sessions attended by participants out of total FB sessions offered during the target intervention duration of 6 weeks.

*Acceptability* will be defined as the ability to deliver a culturally and resource-appropriate intervention. Acceptability will be assessed through brief exit interviews with all patient participants (n=75), HIV providers treating patients in the FB protocol, professional counselors (n=3), lay counselors (n=3), and supervising Master Trainers (n=1 per clinic, n=2 or 3 total). Exit interviews with patients will occur after the final FB session, while exit interviews with other groups will occur after the end of FB activities at each site. Exit interviews will include both closed and open-ended questions and will assess how easy the intervention was to participate in or deliver, the perceived usefulness of the intervention, and suggestions for improvement. The primary measure of acceptability will be overall participant satisfaction defined by the number of patients who were either very satisfied or somewhat satisfied with the FB among all participants who received the FB. Satisfaction will be measured on a 4-point Likert scale-- 1 indicates high satisfaction and 4 indicates high dissatisfaction.

*Fidelity* will be defined as adherence to the intervention protocol. Fidelity to session content for individual counseling sessions will be assessed by a Master Trainer by using a checklist of counseling session elements either during direct monitoring or using audio recording of up to 3 randomly chosen sessions per counselor. As we have defined in prior work, meeting or exceeding expectations at least 75% of checklist items during each

session will be considered fidelity to the intervention protocol.

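### The professional-versus-lay fidelity contrast rests on a robust variance from six counselors with no small-sample method named, so its interval is likely to be too narrow

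*Combined protocol and SAP*

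**What the plan says.** Section 4.0 opens with "Feasibility, acceptability, and fidelity will be evaluated using descriptive statistics". It then adds one comparison: "We will compare mean fidelity scores between the professional FB and lay FB counselors", under intent-to-treat and "using a robust variance estimator to account for multiple observations per counselor". The cluster is therefore the counselor. The section names no small-sample correction, reference distribution, degrees of freedom, confidence level or software for this contrast.

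The only counselor count is in the acceptability paragraph of the Primary Outcomes text in Section 3.0: "professional counselors (n=3), lay counselors (n=3" in the list of people to be given exit interviews. The fidelity paragraph that follows has a Master Trainer score sessions against a checklist, by direct monitoring or "using audio recording of up to 3 randomly chosen sessions per counselor". That makes six clusters and at most 18 rated sessions.

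Sections 2.2 and 3.0 list fidelity among the primary outcomes of the pilot. Section 2.1 states no specific hypotheses. Section 4.0 says that the pilot looks to the size of effects and their precision, not to tests.

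**The concern.** A cluster-robust variance is justified by a large number of clusters. With three per arm, the plain version is biased downward, because the residuals are taken around arm means fitted to the same three counselors. It is also very variable, and a normal quantile ignores that. The plan is right to recognise clustering by counselor, but the method as written, run with usual software settings, tends to give too narrow an interval. The same 18 scores would also give intervals of clearly different width depending on a setting that the plan leaves open.

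At stake is how precisely the pilot appears to have measured a fidelity difference between counselor types. Differences among six individuals could be read as a difference between cadres.

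**Working it through.** The documents give no coverage or precision figure for this contrast, so there is none to reproduce. The fidelity precision in Section 3.4 concerns a single proportion.

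**Inputs from the documents.** k = 3 counselors per arm, G = 6 clusters, up to 3 sessions each, so N = 18 at most (Section 3.0, Primary Outcomes).

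**Assumptions.** 95% two-sided level, normal scores, equal variances in the two arms and, at first, 3 sessions for every counselor.

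**Step 1, bias.** With equal sessions, each arm mean is the average of its counselor means m_i. The uncorrected sandwich for the difference sums (m_i − arm mean)²/k² over both arms. The unbiased variance sums (m_i − arm mean)²/[k(k − 1)]. The ratio is (k − 1)/k = 2/3.

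**Step 2, reference distribution.** The difference divided by its unbiased standard error follows t on 2(k − 1) = 4 df. An interval with variance multiplier m and critical value c therefore covers P(|t4| < c√m), whatever the within-counselor correlation.

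**Step 3, common settings.** The factor G/(G − 1) = 6/5 gives m = 2/3 × 6/5 = 0.80. The fuller factor (6/5) × (17/16), where 17/16 = (N − 1)/(N − 2), gives m = 0.85.

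| Variance and quantile | m | c | c√m | Coverage | Width of t4 interval relative to it |
|---|---|---|---|---|---|
| Uncorrected, normal | 0.667 | 1.960 | 1.60 | 81.5% | 1.73 |
| 6/5, normal | 0.80 | 1.960 | 1.75 | 84.6% | 1.58 |
| Fuller factor, normal | 0.85 | 1.960 | 1.81 | 85.5% | 1.54 |
| 6/5, t on 5 df | 0.80 | 2.571 | 2.30 | 91.7% | 1.21 |
| Fuller factor, t on 5 df | 0.85 | 2.571 | 2.37 | 92.3% | 1.17 |
| Unbiased, t on 4 df | 1.00 | 2.776 | 2.78 | 95.0% | 1.00 |

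Fitting simulated data with one standard package (4,000 runs) gave 81.2% for a GEE sandwich, 85.5% for clustered least squares with a normal quantile, and 92.4% with t on 5 df. The first and fifth rows differ in width by 1.73/1.17 = 1.48, on identical data.

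**Step 4, departures from the assumptions** (simulation, 400,000 runs per case).

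- *Unequal sessions.* With 3, 2 and 1 sessions per arm and intraclass correlation 0 to 0.3, coverage is 78–79% (uncorrected, normal), 83–84% (fuller factor, normal) and 90–91% (fuller factor, t on 5 df). A t4 interval on counselor means covers 95–96%, as does CR2 with Satterthwaite df (about 3.3).
- *Scores near the ceiling.* With beta-binomial scores on 10 or 20 items and mean 0.90–0.95, the fuller factor with t on 5 df covers 93.4–95.6%. The normal-quantile versions cover 83–89%, and t4 on counselor means covers 95.7–97.2%. At mean 0.75–0.80, the fuller factor with t on 5 df covers 92.3–92.5%.
- *Unequal variances between arms.* At a 4-fold ratio, t4 covers 93.9% and the fuller factor with t on 5 df 90.9%. At a 9-fold ratio, the figures are 92.5% and 89.4%.

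**Step 5, is a corrected variance enough?** No. The unbiased variance with a normal quantile gives P(|t4| < 1.96) = 87.8%, so the degrees of freedom must be named too.

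**The case against.** The strongest reply is that little in the plan depends on this interval. Fidelity is to be described, the pilot states no hypotheses, and no threshold or go/no-go rule is tied to the contrast. An analyst who used t on 5 df with the usual factor would be only a few points short, and less than that if most sessions score near the maximum. All of this stands, and it limits the consequence. It does not remove the point, because Section 4.0 makes precision the aim of the pilot and this interval would misstate it. Nothing in the plan steers the analyst away from a normal quantile, and the shortfall with a normal quantile persists even with scores near the ceiling.

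Three stronger readings are tempting.

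- A reader might infer that this interval would steer investment in trained counselors. Section 1.2 says that "the MOH could invest in expanding this cadre if evidence suggests that the higher level of training is critical", and Section 4.0 sets its effectiveness analyses as "comparing professional counselors to enhanced usual care and lay counselors to enhanced usual care", so the fidelity contrast is the only one there that names professional against lay directly. But the Section 1.2 passage is about whether counseling works, not about checklist fidelity, and it goes on to say that the pilot is to inform a larger trial.
- A reader might infer that any software would under-cover. No software is named, and CR2 with t on 4 df reaches 95% under the assumptions above. The range describes common settings only.
- A reader might dismiss the contrast as exploratory. The documents do not call it that; it compares a primary outcome.

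**Conclusion.** The point holds and is worth changing. With six counselors and no finite-sample method named, a nominal 95% interval for the professional-versus-lay difference in mean fidelity covers about 82% to 92% under the common settings examined. This assumes normal scores, equal variances and equal sessions. With 3, 2 and 1 sessions per arm the range is about 78% to 91%. With scores near the ceiling the t5 version is close to adequate, and only the normal-quantile versions clearly fail. The documents give no expected mean score or session balance, so the shortfall under a t reference cannot be fixed more closely. The range also depends on the stated count of three counselors per type.

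The effect is limited to the reported precision of this one contrast. A reader might infer that the pilot's fidelity finding as a whole is unsound. The documents do not support that: the descriptive summary against the 75% checklist standard does not use this variance, and the plan draws no confirmatory conclusion from the contrast.

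**What to change.** In Section 4.0, replace the generic robust variance for this contrast with a t interval on the six counselor-level mean fidelity scores (3 versus 3, 4 df), and report each counselor's score beside it. This weights counselors equally. If a mean that weights sessions equally is wanted, say so and use a CR2 variance with Satterthwaite degrees of freedom. With equal sessions the two coincide; with unequal sessions they estimate different quantities, so the plan should choose one in advance.

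The change takes one or two sentences and no new data. The interval becomes about 1.2 to 1.7 times as wide as under the common settings with equal sessions, and about 1.3 to 2.0 times with 3, 2 and 1 sessions per arm. The t4 interval under-covers mildly (about 92.5% to 94%) if variances differ strongly between arms, and is slightly conservative for scores near the ceiling.

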### 2.2 Study Objectives

**AIM 1:** To adapt the proven Friendship Bench (FB) protocol to be optimized for PLWH and OUD in Vietnam.

**Key outcome of Aim 1.** The primary outcome of Aim 1 will be the finalized revised FB protocol that is adapted for PLWH and OUD in Vietnam.

**AIM 2:** To assess the feasibility, fidelity, and acceptability of the adapted FB as well as preliminary indicators of its impact in improving CMD and engagement in HIV care and drug use treatment via a small three-arm individually randomized trial, comparing FB by professional counselors to FB by lay counselors to enhanced usual care for PLWH and OUD with CMDs.

The **primary outcomes** of the pilot trial will be the feasibility, acceptability, and fidelity of delivery of the adapted FB protocol. **Secondary outcomes** will include preliminary indicators of impact of the adapted FB protocol in improving HIV-related outcomes (eventual R01 primary outcomes) and MMT and mental health outcomes (eventual R01 secondary outcomes).

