protocol. Feedback from this review will inform the development of the next draft of the protocol. In steps 7 and 8, an interventionist will be trained and this second draft will be piloted with 5 eligible patients to further refine session content. The process will culminate with a final version of the adapted FB protocol that will be ready for formal evaluation in Aim 2 in a three-arm pilot study.

**AIM 2: To assess the feasibility, fidelity, and acceptability of the adapted FB as well as preliminary indicators of its impact in improving CMD and engagement in HIV care and drug use treatment via a small three-arm individually randomized trial, comparing FB by professional counselors to FB by lay counselors to enhanced usual care for PLWH and OUD with CMDs.**

**Study Design.** We will complete a pilot trial in which we will randomize 75 eligible patients to either the FB by a professional counselor (n=25), or FB by a lay counselor (n=25), or enhanced usual care (n=25). Patients will be enrolled from 4 MMT clinics under CDC Hanoi jurisdiction and with which we have previous successful collaborations. Patients meeting full eligibility criteria (see below) will be invited to provide written informed consent to participate in the study. As a pragmatic effectiveness trial, the purpose of the eventual R01 will be to compare the effectiveness of the adapted FB protocol delivered by a professional counselor and delivered by a lay counselor relative to enhanced usual care in improving HIV/MMT care engagement and outcomes (primary outcomes for the future trial). Therefore in this pilot, consenting participants will be individually randomized in the same way, to one of those three arms (described below).

[figure not shown]

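### Must Section 4.0 name a lay-versus-professional effectiveness contrast with its own interval?

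*Combined protocol and SAP*

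**What the plan says.** Section 4.0 sets out the effectiveness contrasts in one sentence: "We will evaluate effectiveness measures comparing professional counselors to enhanced usual care and lay counselors to enhanced usual care". The direct professional-lay pair is named once in that section, for a delivery outcome: "We will compare mean fidelity scores between the professional FB and lay FB counselors using an intent-to-treat approach".

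Two further statements in Section 4.0 are general. Means and proportions for the HIV and mental health outcomes are to be compared across arms by intention to treat. GEE models are to be fitted "to simultaneously examine differences in outcomes at 6 weeks, 3 months, 6 months and 12 months between the arms". Neither lists pairs. The section puts its weight on effect size and precision, not on testing.

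Elsewhere, Aim 2 (Section 2.2) describes a trial "comparing FB by professional counselors to FB by lay counselors to enhanced usual care". Section 1.2 says of professional counselors that "the MOH could invest in expanding this cadre if evidence suggests that the higher level of training is critical", and then: "However, if lay counselors are equally effective then their deployment would be less expensive". The objective at the end of Section 1.2 sets both delivery modes against enhanced usual care (EUC). Section 3.0 (Study Design) gives the purpose of the later full-scale trial as comparing each delivery mode "relative to enhanced usual care in improving HIV/MMT care engagement and outcomes". Section 2.1 states that the pilot has no specific hypotheses.

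**The concern.** The authors named the professional-lay pair where they wanted it for fidelity and did not name it for patient outcomes. Yet the choice between counselor cadres is part of the reason for having two Friendship Bench arms. A plan built on estimation might be expected to list the estimates that bear on that choice.

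There is also a technical point. The lay-professional point estimate follows from the two EUC contrasts, because the EUC arm cancels. Its interval does not follow from the two EUC intervals alone, because both contrasts share the EUC arm and are therefore correlated. If a report gave only those two intervals, readers might compare them by eye, or rank the counselor types by which interval excludes no effect. Either habit could support an unwarranted statement that lay counselors are, or are not, as good as professionals.

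**Working it through.** **Inputs.** Randomization is 1:1:1 with 25 per arm (Section 3.0). Retention of 80% (Section 3.4) leaves 25 × 0.80 = 20 per arm. There are three counselors of each type (Section 3.0, Primary Outcomes). The documents give neither outcome risks for the two Friendship Bench arms nor a within-counselor correlation (ICC), so those values below are assumptions.

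**The plan's own precision figure.** Section 3.4 illustrates a risk ratio of 0.63 with limits 0.38 to 1.00. No control risk is stated. Counts of 10/20 against 16/20 come close:

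- RR = 0.50/0.80 = 0.625
- SE of log RR = √(1/10 − 1/20 + 1/16 − 1/20) = √0.0625 = 0.25
- limits 0.625 × exp(±1.96 × 0.25) = 0.38 to 1.02, about 2.7-fold

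So the plan's figure fits 20 per arm and a control risk near 0.80.

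**Can the third pair be estimated from what is planned?** Take the outcome SD as 1.

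- Each EUC contrast has variance 1/20 + 1/20 = 0.10.
- Their covariance is the variance of the shared EUC mean, 1/20 = 0.05, so their correlation is 0.5.
- Lay minus professional has variance 0.10 + 0.10 − 2 × 0.05 = 0.10 and SE 0.316.

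A model holding all three arms supplies that covariance, so the third contrast is a linear combination of coefficients already fitted. With a log link it is the ratio of the two risk ratios. For unadjusted results the model is not even needed: arm-level proportions with denominators, or means with SDs and denominators, give the interval directly.

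**How much would it say?**

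- Continuous outcome: 1.96 × 0.316 = ±0.62 SD (±0.64 SD with the t quantile on 38 df).
- Binary outcome, true RR 1, common risk p: SE of log RR = √(2(1 − p)/(20p)), and risk-difference half-width = 1.96 × √(2p(1 − p)/20).

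| Assumed risk in both arms | RR limits | Risk difference |
|---|---|---|
| 0.3 | 0.39 to 2.58 | ±28 points |
| 0.5 | 0.54 to 1.86 | ±31 points |
| 0.8 | 0.73 to 1.36 | ±25 points |

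**Counselor clustering.** The average caseload is 20/3 = 6.67, and the design effect is 1 + 5.67 × ICC.

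| Assumed ICC | Design effect | SE (SD) | ± with normal quantile | ± with t on 4 df (2.776) |
|---|---|---|---|---|
| 0.05 | 1.28 | 0.358 | 0.70 | 0.99 |
| 0.10 | 1.57 | 0.396 | 0.78 | 1.10 |

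Six counselors less two groups leave 4 df, so the last column is the more realistic guide.

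**Match to the stated purpose.** The objective in Section 1.2 and the purpose of the later trial in Section 3.0 are both framed against EUC, as are the two named contrasts. The remark in Section 1.2 about lay counselors is a conditional about cost, not a study question. The clinical worry beside it is that professional skill may be needed for the intervention to work at all in this population, and the lay-EUC contrast addresses that.

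**The case for a change.** The best case for a change is that the gap is real in the text and cheap to close. The plan shows that its authors name this pair when they mean it. General wording about arms does not say which pairs receive an interval. The general sentence on means and proportions also leaves out methadone engagement, so for that outcome even the loose wording gives less cover. One added contrast per fitted model needs no new data, and a visibly wide interval would warn readers against claiming that the counselor types are equivalent.

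What stands is that the pair is not named and that its interval cannot be built from the two EUC intervals alone. The rest is weaker:

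- Combining the two EUC contrasts as if independent would give an SE of √(4/20) = 0.447 SD in place of 0.316, but the plan does not propose this.
- Ranking arms by which interval excludes no effect is a significance reading, and Section 4.0 turns away from that.
- The harm requires a report showing only the two EUC intervals. The plan also calls for means and proportions by arm, though it does not promise SDs.
- A contrast taken from the same models without allowance for counselors could itself be too narrow, so naming it would not by itself give a sound statement about counselor type.

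**Conclusion.** No change is needed. Followed as written, Section 4.0 gives sound estimates of the two effects that the pilot and the later trial are about. The unnamed pair is a detail that the general wording permits and that an analyst can supply from the same data. No decision rule, sample size or claim in the documents depends on it.

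The information at stake is small: about ±0.62 SD at 20 per arm before any allowance for counselors, and about ±1.0 to ±1.1 SD once three counselors per type and a t quantile on 4 df are taken into account. The first figure rests on 80% retention and equal SDs, and the second also on assumed ICCs of 0.05 to 0.10. An interval that wide could not support a statement that lay and professional counselors are equally effective, whether or not the plan names it. If the authors choose to report it, it is descriptive only and not evidence of equivalence.
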